Interpersonal Needs Questionnaire (INQ)	PV	✓		✓	Self-report measure that assess thwarted belongingness and perceived burdensomeness (Van Orden et al., 2012). The INQ has demonstrated good convergent validity, internal consistency and concurrent validity (Van Orden et al., 2012).
Treatment Involvement Form (TIF)	CV	✓	✓	✓	Form created for the current study that will be used to assess treatment involvement during the prior interval, including medical, psychiatric and psychological treatment, as well as supportive interventions (e.g.

					Alcoholics Anonymous, Narcotics Anonymous).
Columbia Suicide Scale	DV	✓		✓	The Columbia Suicide Scale (Posner et al., 2008) is a state-of-the-art suicide assessment for individuals perceived to be at high risk for suicidality. Internal consistency ranged from .73 to .95 (Posner et al., 2011).
Clinician Administered NSSI Disorder Index (CANDI)	DV	✓		✓	The CANDI is a clinical interview that diagnoses Nonsuicidal Self Injury (NSSI) disorder and type and frequency of NSSI. Demonstrated good reliability and validity in prior research, including in Co-I [name]'s VA-funded study of NSSI in veterans. Administered in tandem with the NSSI Screen developed by Co-I [name].
Beck Scale for Suicide Ideation (BSSI)	DV, Med	✓		✓	Widely-used self-report measure of intensity of thoughts and behaviors associated with suicide. Includes 2 additional items that ask about past suicide attempts as well as the level of suicidal intent during the most recent attempt. Prior research shows that endorsement of suicidal thoughts and behaviors can be greater on self-report questionnaires compared to interviews. Thus, this measure complements the suicide focused interviews.
Suicide Cognitions Scale-Brief	DV, Med	✓		✓	Self-report measure of suicide-related thoughts that load onto the following subscales: unsolvability, unlovability, and unbearability. Brief version was recently validated across 3 chronic pain samples (Bryan et al., 2016).
PTSD Checklist-5 (PCL-5)	Med	✓	✓	✓	Self-report of symptoms of PTSD during the previous month. Demonstrates high sensitivity and specificity in relation to a lengthy diagnostic interview for PTSD (CAPS), with which it was co-developed. Strong psychometric properties, including in numerous Project SERVE papers.

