Patient Health Questionnaire-9	Med, DV	✓	✓	✓	Self-report measure used for screening, diagnosing, and monitoring depression. It incorporates DSM-IV diagnostic criteria (Question 9 screens for suicidal ideation; Kroenke, Spitzer & Williams, 2001).
Alcohol Use Disorders Identification Test (AUDIT)	Med	✓	✓	✓	Self-report measure to screen for alcohol-use disorders (Saunders, Aasland, Babor, Fuente, & Grant, 1993). 10-item measures adopted by VA as the gold-standard screening for alcohol use disorders in mental health and primary care clinics. Good internal consistency ( $\alpha=.80$ - .94) and test-retest reliability ( $r=.86$ ), and strong concurrent validity with the MAST and CAGE screening measures (Babor et al., 2001).
Drug Abuse Screening Test (DAST)	Med	✓	✓	✓	Self-report measure to quantify drug misuse and related psychosocial impairment. Good internal consistency and concurrent validity with frequency of drug use over 12-months (Skinner, 1982). Moderately correlated with denial and social desirability. The instructions will be updated to more explicitly assess for misuse of opiates that may have been prescribed.
Substance Use Screen	Med	✓		✓	Form created for the current study that will be used to assess current and lifetime substance use (e.g., stimulants, cannabis, etc.)
TBI—Vasterling Assessment Interview	E, Med	✓		✓	This clinician-administered structured interview developed by Vasterling (2008) assesses the number, recency, type of injury, and clinical sequelae associated with traumatic brain injury during deployment. Total number of lifetime head injuries leading to any symptoms will also be assessed. TBI will be assessed at baseline for lifetime history and then re-assessed at the annual interview for any new TBIs that may have occurred during the past two years.
Ten-item Personality Inventory (TIPI)	PV	✓			10-item self-report measure of the Five-Factor Model of personality (Gosling, Rentfrow & Swann, 2003).
Patient Health Questionnaire-15 (PHQ-15)	Med, DV	✓		✓	Self-report (Kroenke, Spitzer & Williams, 2002) of somatic symptom clusters including pain (musculoskeletal, headaches), cardiac, gastrointestinal, respiratory, etc. that account for more than 90% of outpatient physical complaints (Kroenke, Arrington & Mangelsdorff, 1990). The PHQ-15 had strong internal reliability in the initial validation ( $\alpha=.80$ ) and was associated with functional status and disability (Kroenke et al., 2002).

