Working Alliance Inventory	PV			Widely-used, brief self-report measure of clients' perceptions of working alliance with therapist on 3 dimensions: goal, task, and bond (Horvath, 1981).	
Parenting Stress Index Short Form (PSI-SF)	PV	✓	✓	✓	Veterans with a child between birth and 12 will be asked to complete this measure on the child they are most concerned about. Thirty-six items are divided into three domains: Parental Distress (PD), Parent-Child Dysfunctional Interaction (P-CDI), and Difficult Child (DC), which combine to form a Total Stress scale.
Quality of Marriage Index (QMI)	PV	✓	✓	✓	6-item self-report questionnaire used to measure relationship distress (Norton, 1983). The measure was developed based on an empirical analysis of the functioning and construction of marriage quality variables.
Saliva sample and saliva collection questionnaire	PV, Med	✓			DNA and other products will be extracted from saliva samples. A list of 13 questions will be asked during sample collection related to variables that can affect quality of saliva sample and associated biomarkers (e.g., time since last meal). Provision of saliva sample is optional.
Blood sample	PV, Med	✓			DNA and other products will be extracted from blood samples. Provision of blood sample is optional.

BL = Baseline; E = Eligibility; DV = Dependent/Outcome Variable; PV = Predictor Variable; Med = Mediator; CV = Covariate

**Training of Clinical Interviewers.** Clinical interviews will be conducted by trained interviewers familiar with the assessment procedures and the culture of military service. The PI and trained doctoral staff members will conduct certifications in the proper administration of the clinical interviews and will provide ongoing, weekly supervision of interviews conducted. Further, all interviews will be video or audio-recorded through a VA computer using a microphone directly onto the secure, approved drive behind the VA firewall or using a FIPS 140-2 validated digital voice recorder. In any instance in which technical or logistical difficulties interfere with video recording, audio recording will be used. All video/audio files will be stored on the secure, approved drive

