## **Analytical Plan.**

**Aim 1:** The proposed analyses are grounded in the SERVE conceptual framework (Figure H1a). Our team has expertise in a variety of advanced statistical modeling procedures, including latent growth models, growth mixture models, longitudinal analyses, and measurement invariance. The design is based on a measurement model that collects predetermined, repeated assessments every 8 months over a two-year period. The effect of treatment will be examined via dummy variables in all hypotheses. We will use both traditional (e.g., maximum-likelihood regression) and advanced approaches (e.g., latent growth models, growth mixture models, and mediation models with bias-corrected bootstrap confidence intervals) to analyze the data. For example, to test Hypothesis 1a (H1a) in a traditional manner, principal component analysis (PCA) will be used to create a composite functional impairment factor. This approach will greatly reduce the number of tests conducted and provide us with a broad index of functional impairment. Variables used to create this factor score will include measures of functional impairment (WHODAS 2.0, IPF), QoL (QLS), and values-based behavior (VT). Change scores for these measures will be calculated and regressed onto the hypothesized predictors and covariates (including prior level of functional impairment) to test H1a. Latent growth modeling (LGM)—which allows for modeling of the change/growth trajectory of different variables assessed on multiple occasions across time—will also be used to analyze the data. We expect that scores on repeated measures will be correlated. Growth models take this dependency into account by treating repeated measures as separate variables, and fitting a proposed trajectory shape to the scores across time. Advantages of using LGM over other approaches include the flexibility of placing constraints on the model while allowing growth parameters describing participants' trajectories to serve as predictors or outcomes. LGM assumes that individuals come from a homogeneous population while Growth Mixture Modeling (GMM) allows multiple subpopulations to be inferred from the data. GMM is a general latent class analytical framework that has the capacity to model both random variation of the latent growth factors and the unknown heterogeneous subpopulations simultaneously. The proposed mediation effects will be examined with bias-corrected bootstrap confidence intervals that have been shown to produce the unbiased test with highest statistical power. We will ensure adequate data quality by evaluating normality and conducting descriptive, outlier, and psychometric analyses for each data wave. We will use alternative robust estimators (e.g., WLSM, WLSMV, MLM, and MLMV) when analyzing non-normal data. All SEMs including the LGM and mediation analyses will be evaluated with the chi-square test and commonly used fit indices such as RMSEA, SRMR, CFI and TLI. Additionally, for GMM, we will evaluate the results using the recommended information criteria (e.g., BIC, BLRT) and other related fit statistics (e.g., entropy). Analyses will be registered in the NIH clinical trials online database prior to data collection.

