
The statistical power of the hypothesized models was estimated using the Monte Carlo procedure in Mplus. For each power analysis, 1000 datasets were simulated following a hypothesized model that included a particular effect size of interest for each test. The model(s) of interest were then estimated for each dataset, and the proportion of datasets in which the null hypothesis was rejected was taken as the (empirical) power of the test. To examine the effect of the novel and established treatment targets on functional impairment over time in Hypothesis 1a, we will use LGM with the treatment targets measured at baseline predicting functioning

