over time (Figure H1a). The statistical power of the target effect, the direct arrow from the treatment targets to the slope of functional impairment over time, is evaluated. Given the proposed sample size (500 participants with 4 repeated measures), the power for detecting a medium direct effect (based on our preliminary analyses) from the treatment targets to the slope of functional impairment is  $> .90$ . GMM will be used to test Hypothesis 1b (Figure H1b). Based on our preliminary studies, the statistical power for detecting a three-class solution is larger than .90 given the proposed sample size (500 participants). We calculated statistical power for the effects of the novel and established treatment targets on latent class membership. Assuming a small to medium effect size (odds-ratio = 1.82, which roughly corresponds to Cohen's  $d$  of 0.34), the power of the treatment targets on predicting class membership ranged from .72 to .91. In Hypothesis 1c, risk for SDV is measured in multiple ways including a continuous variable (severity of suicidal thoughts), a frequency/count variable (number of instances of NSSI), and a dichotomous variable (attempted suicide). A latent factor will be created and analyzed in Mplus which uses the MLR estimation to handle non-normally distributed variables. The longitudinal property of this latent factor will be examined via the longitudinal measurement invariance. Once the risk for SDV factor model is confirmed, we will regress it on the latent class membership (based on H1b results), hypothesizing that the most severely impaired class will predict greater risk of SDV. The proposed mediation model in Hypothesis 1d (i.e., the treatment targets mediate the effects of mental and physical wounds on functional impairment and risk for SDV over time) will be tested by using Mplus MODEL INDIRECT with bootstrap confidence intervals. By assuming a medium mediation effect, the corresponding statistical power is larger than .80 with our proposed sample size. We used conditions and parameters that are broadly based on our own data, prior clinical studies, and published Monte Carlo studies. Effect sizes estimates were in the small-to-medium range. The number of repeated measures is based on the current design. In brief, we are confident that the parameters and conditions are very close to our proposed study conditions.

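### Hypothesis 1d needs the INQ and MIES as mediators, but their schedule cannot place them between wound and outcome, and Table 1 codes wounds and targets in the opposite roles

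*Combined protocol and SAP*

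**What the plan says.** The Analytical Plan for Aim 1 introduces H1d in a parenthesis: "the treatment targets mediate the effects of mental and physical wounds on functional impairment and risk for SDV over time". The test is Mplus MODEL INDIRECT with bootstrap confidence intervals. Power is put above .80 for a medium mediation effect at the proposed sample of 500. This text gives no wave for the wound, the target or the outcome. H1a does give one: "we will use LGM with the treatment targets measured at baseline predicting functioning" over time.

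Aims and Hypotheses lists five conditions (PTSD, depression, chronic pain, TBI, AUD), four novel targets (mindfulness, burdensomeness, belongingness, moral injury) and three established ones (psychological flexibility, self-compassion, emotion regulation).

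The Table 1 legend defines the codes: "PV = Predictor Variable; Med = Mediator; CV = Covariate".

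Two sources that might add detail are outside the available text. The plan says "The proposed analyses are grounded in the SERVE conceptual framework (Figure H1a"; that figure is not shown. It also says "Analyses will be registered in the NIH clinical trials online database prior to data collection"; that record is not among the documents.

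**The concern.** A mediation claim is a claim about order: the wound comes first, then the target, then the outcome. Two things stand in its way.

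First, H1d and Table 1 state rival orders. Data from one visit cannot say which is right, so the plan has to.

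Second, a mediator should be measured after the wound and before the outcome. For three of the four novel targets no such measurement is scheduled. If wound and target come from the same visit, a stable trait behind both can produce a significant indirect effect with no mediation at all. Since Aim 1 is to identify treatment targets, such a result would be read as a reason to treat that target.

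**Working it through.** **1. The plan's own figure.** The H1d power (> .80) is given without path values or alpha, so it cannot be reproduced strictly. As a plausibility check, take the product of the power for each path, with standardized a = b, no direct effect and two-sided alpha .05 (all assumed):

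- SE(a) = √[(1 − a²)/n] and SE(b) = √[(1 − b²)/(n(1 − a²))].
- At a = b = .143 and n = 500, SE(a) = .0443 and SE(b) = .0447, so z = 3.23 and 3.20.
- Power = Φ(3.23 − 1.96) × Φ(3.20 − 1.96) ≈ .898 × .892 = .80.
- At a = b = .20 power is .99; at .30 it exceeds .99.
- With n = 400 (500 less 20%), .80 is reached at a = b of about .160.

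The stated figure is therefore plausible for a medium effect.

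**2. Roles and waves in Table 1.** The protocol does not map constructs to scales. The mapping here follows the scale descriptions.

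| Role under H1d | Measure | Table 1 code | 8 and 16 months? |
|---|---|---|---|
| Wound | PCL-5 | Med | yes |
| Wound | PHQ-9 | Med, DV | yes |
| Wound | AUDIT | Med | yes |
| Wound | TBI interview | E, Med | no |
| Wound | Chronic pain screen | Med | no |
| Target | AAQ-II, BEAQ, SCS-SF, DERS-Brief, FFMQ | PV | yes |
| Target | INQ | PV | no |
| Target | MIES | PV, repeated if re-deployed | no |

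Five of five wound measures carry Med and none carries PV. All seven target scales carry PV alone. The TBI interview was E, PV in the Phase I and Phase II tables and is E, Med in Phase III, so carry-over does not explain that code.

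**3. What the schedule allows.** With a baseline wound and a 24-month outcome, the INQ can share a visit with one or the other but cannot lie between them. The MIES is in addition a record of earlier events, so current symptoms cannot act through it. The other five scales have 8- and 16-month values. The self-directed violence (SDV) measures (Columbia, CANDI, BSSI) are at baseline and 24 months only, so 24 months is the only later SDV wave.

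**4. Order at a single visit.** Data were simulated with the target causing the wound (r = .30) and both affecting the outcome by .14. The H1d order was significant in 86% of datasets at n = 500 and 78% at n = 400; the reverse order in 85% and 79%. With direct paths of .30 both orders reached 100%.

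**5. Shared stable cause, no mediation.** Assume that wound W, target T and outcome Y at 0, 8, 16 and 24 months each equal λU + √(1 − λ²)·e. U is one fixed trait and e is an AR(1) residual with correlation ρ between waves. N = 500; both paths tested at 5%. Models:

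- same visit: T0 on W0, Y0; Y24 on T0, W0, Y0
- lagged: T8 on W0, T0, Y0; Y24 on T8, W0, T0, Y0
- two-wave: T24 on W0, T0, Y0; Y24 on T0, W0, Y0
- slope: T0 on W0; each person's four-wave slope of Y on T0, W0, without baseline adjustment

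False-positive rates (%) at λ = 0.3 / 0.5 / 0.7:

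| Model | ρ = 0.5 | ρ = 0.8 |
|---|---|---|
| Same visit, baseline-adjusted | 15 / 91 / 100 | 7.5 / 62 / 93 |
| Lagged, baseline-adjusted | 2 / 26 / 65 | 0.5 / 3 / 9 |
| Two-wave | 10 / 84 / 100 | 3 / 39 / 88 |
| Same visit, unadjusted slope | 2.4 / 4.8 / 4.9 | 2.4 / 5.3 / 6.0 |

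A repeat with new random numbers agreed within about 2.5 percentage points. With no shared cause, the three baseline-adjusted models are at 0.4% or less. The plan's change-score regression, which covaries prior impairment, behaves like the first row: moving Y0 to the left-hand side changes only the coefficient of Y0. The slope removes a trait with constant loading because slope weights sum to zero. A random-intercept cross-lagged model gave 0.7 / 0.7 / 0.3% at ρ = 0.5, a best case because it matches the simulated truth.

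**6. Power of the lagged model.** Assume baseline correlation 0.4, target stability 0.6, outcome stability 0.48 and a wound-to-outcome path of 0.1. At a = b = 0.10 / 0.15 / 0.20, power is 39 / 85 / 98% at N = 500 and 29 / 74 / 96% at N = 400. The N = 400 figures treat 20% missing as complete cases, which is harsher than the planned FIML.

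**The case against.** **The simulation may not describe the plan's model.** The main longitudinal method is latent growth modelling, with H1a's key path going to the slope. On that reading a same-visit model stays near 5%, while the lagged model reaches 65% in the worst case. This stands: lagging is not uniformly better, and the high rates cannot be pinned on H1d in general. But H1d does not say that its outcome is the slope, the plan also describes baseline-adjusted change scores, and SDV has only two waves. A slope model also cannot show whether wound or target came first.

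**The waves may be stated elsewhere.** A reader might infer that the plan leaves H1d's timing open. The documents do not support that, because Figure H1a or the registration may fix it. Neither could add an INQ wave.

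**The code mismatch is largely editorial.** PV is correct for the targets under H1a and H1b, so what is missing is a second label. Related scales (FREE, DES-IV, Social Connection Index, Brief Loneliness Measure) are coded DV, Med. This largely stands. But none of these shows 8- and 16-month ticks as far as the table can be read, so they do not fill the gap.

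**The INQ has earlier data.** Phase II collected it at baseline with the PCL-5, PHQ-9, AUDIT and Columbia scale. For transfers from Phase II, an ordered chain is possible: Phase II wound, Phase III baseline INQ, 24-month SDV. This stands as support in a subset whose size is not given. The IMPACT section expects 210 impaired transfers, but not all need come from Phase II.

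**Conclusion.** The point holds and should be fixed, with medium confidence. The firm part rests on the documents alone: H1d needs mediation paths that the MIES cannot carry and that the INQ cannot carry in time order within Phase III, and these scales cover three of the four novel targets. The role codes contradict H1d for all five wound measures and all seven target scales, but that alone would be minor.

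The false-positive rates are illustrative. They depend on assumed loadings and stabilities and apply to outcomes adjusted for baseline level, not to an unadjusted growth slope. A reader might infer that H1d findings would mostly be spurious, or that the study is underpowered for H1d. Neither follows: the outcome form is not settled in the visible text, and the stated power is plausible for the effect it assumes.

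**What to change.** 1. Use the MIES as a baseline predictor only. Label any INQ mediation exploratory and not temporally ordered within Phase III; linked Phase II data for transfer participants may be used as support.
2. For the AAQ-II, BEAQ, SCS-SF, DERS-Brief and FFMQ, take the wound at baseline, the target at 8 or 16 months adjusted for its baseline value, and the outcome at a later wave. Name the wave and the primary paths: 5 wounds × 5 scales × 2 outcomes gives 50 candidates. If Figure H1a or the registration already states the waves, copy them into the H1d text.
3. State whether the functioning outcome is the growth slope or the 24-month score. Where four waves exist, report a random-intercept cross-lagged or slope-based model as a sensitivity analysis, and say that a lagged model adjusted for baseline outcome reduces stable-trait confounding but does not remove it.
4. Align Table 1: PV, Med for targets used as mediators, PV for the wounds (keeping DV on the PHQ-9 and E on the TBI interview). The MIES stays PV.
5. Restate H1d power for the chosen model at 500 and with 20% missing.

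The cost is table codes, analysis-plan wording and one power re-run, with no new data collection. The downsides are lower power if the lagged paths are near 0.10, loss of the moral-injury mediation claim, and an INQ claim that is exploratory at most.

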## HUMAN SUBJECTS RESEARCH AND PROTECTION FROM RISK

### 1. Risks to Subjects

A. Human Subjects Involvement and Characteristics: Up to 600 male and female OEF/OIF/OND Veterans enrolled for healthcare at the CTVHCS will be participants in Phase III. Veterans from all races/ethnic backgrounds will be recruited. Veterans with mental health conditions will be over-sampled. Participants will be

Figure H1a

[figure not shown]
[figure not shown]

Figure H1b

at least 18 years of age. The telephone screen will determine initial study eligibility. Eligible participants will be scheduled for a baseline assessment, at the beginning of which participants will complete a written informed consent form (ICF) for all Phases. Final eligibility will be confirmed at the baseline assessment. Participation is voluntary, with no penalty for withdrawal. Consistent with HIPAA and institutional IRB guidelines, the utmost care will be taken to protect the welfare and interests of human subjects. All key personnel are thoroughly trained in the conduct of human-subjects research. See also below “Protection Against Risk” and “Data Safety and Monitoring Plan.”

B. Sources of Material: The baseline and annual follow-up assessments will be collected by questionnaire, clinical interview, and saliva/blood samples. In addition, questionnaire follow-up assessments will be mailed to participants 8- and 16-months post baseline; the Veteran will have the option to complete the follow-up assessment either by paper and pencil or online through Qualtrics. Participants who prefer to receive email reminders via the Qualtrics system will have their email addresses temporarily stored in the secure Qualtrics database using the “Contact List” feature. The Contact List is a feature within a PI’s individual, password protected, online Qualtrics account. This feature allows the PI and approved study personnel to create a list of study participant email addresses. Only through this feature are study personnel able to send a survey link via an email from Qualtrics to participant’s who request this method. Only approved study staff will have access to this online account and will be able to enter or see participant’s email addresses. No PHI will be sent or received using this feature. The Contact List will simply store email addresses and this feature will allow for the distribution of survey links to every participant, which will not require participants to provide any identifying information. All email addresses will be deleted from the Qualtrics Contact List at the completion of the study. For further description of the Qualtrics security structure, please see the “Qualtrics Security White Paper.” All data will be collected for research purposes only. The data will be protected as mandated by local IRB committees and the national HIPAA guidelines. Face-to-face interview and questionnaire data obtained during baseline and follow-up assessments by the research team will be stored in locked files with only code numbers to identify participant data. A list linking names with code numbers will be kept to ensure that no participants re-enter the protocol and to facilitate scheduling for follow-up assessments; this list will be kept electronically on the secure research drive. All research staff involved with the study will be made fully conversant with relevant ethical principles related to the conduct of human subjects research (including completion of HIPAA training and CITI training in human subjects research) and will be trained to be sensitive to the potential need for clinical referral.

In the event that an assessment conducted by members of the research team indicates that a participant is severely debilitated and/or needs a clinical referral (e.g., reports suicidality, homicidality, and/or severe symptomatology), the assessor will conduct a risk assessment, develop a safety plan (if necessary), and make an appropriate clinical referral. The PI will be notified of all such occurrences immediately. All CoE staff have been fully trained by a doctoral-level staff member or the local suicide prevention coordinator using the Operation SAVE (Signs, Ask, Validate, Encourage) program developed by the Canandaigua CoE. Emergency response (i.e. if the Veteran is actively suicidal or homicidal warranting crisis intervention) varies based on the campus in which the Veteran is being interviewed. In Waco, during regular business hours, Veterans can be escorted to the Mental Health Clinic for further evaluation, stabilization and hospitalization as necessary. After business hours, staff is instructed to call 911. In Temple, Veterans in crisis are brought to urgent care for evaluation, stabilization and hospitalization as indicated. In Austin, staff is instructed to call 911, as no emergency services are available on site. However, Veterans who would like immediate outpatient services can be referred to Primary Care Mental Health in Austin for same-day outpatient appointments.

In the event that a follow-up assessment received in the mail, online, telephone, or by VA approved video communication technology indicates that a participant is severely debilitated and/or needs a clinical referral (e.g., reports suicidality and/or severe symptomatology), the assessor will contact the PI immediately. The PI or trained staff member will then contact the participant to conduct a risk assessment, develop a safety plan (if necessary), and provide appropriate local treatment referral(s).

With respect to connecting Veterans with appropriate mental health services, a system of providing clinical referrals across each campus in which Veterans will be interviewed (Waco, Temple, Austin) has been established during the Project SERVE pilot study and continued in subsequent Phases. We anticipate that some Veterans will refuse referrals, particularly in light of data suggesting strong concerns about stigma among returning OEF/OIF Veterans (Hoge et al. 2004). We will make every effort to make Veterans feel

connected to the research study, which we hope will serve as an additional point of access to clinical services offered at CTVHCS. By establishing a relationship, coupled with data-driven check-ins on an ongoing and as-needed basis, we hope that Veterans who initially refuse services will eventually feel more comfortable accepting referrals. Certainly, study staff will be available at all times to forge a liaison with mental health services upon request.

In addition to interviews and self-report questionnaires, saliva/blood samples will be collected from participants. All specimens will be used strictly for research purposes. Providing a saliva/blood sample is optional and declining to provide a saliva/blood sample does not impact participation in the rest of the study.

With respect to the saliva sample, staff will be trained to avert their eyes when participants are spitting into the test tube to reduce the risk for potential embarrassment. The procedure will take approximately 1 minute. With respect to the blood draw, risks will be minimized by using personnel trained by the VA who will have a fully self-contained phlebotomy kit for each participant. Personnel draw 19 ml (= 4 teaspoons) of blood. The procedure will take approximately 10-15 minutes. Samples will be labeled with code numbers only and transported by study staff to the Waco VA Campus (Building 93: room 2A 113) for DNA extraction and storage. Participants will complete a layered informed consent process in which they will be informed of all procedures and will be given the opportunity to participate in the larger observational study while opting out of providing saliva/blood samples for later studies. Further, participants may specify that their DNA samples may not become part of the shared dataset/tissue repository.

C. Potential Risks: Potential risks include breach of confidentiality, coercion to participate, and possible discomfort from processing and retrieving memories of traumatic events. There is also some concern that a seriously impaired Veteran could be identified by the measures included in the interviews or the self-report questionnaires. As discussed in greater detail below, we believe that the likelihood of breach of confidentiality and coercion are low, given the steps we have taken to obviate these risks (e.g., numeric coding, informed consent). This study assesses sensitive information (e.g. alcohol and drug history). To protect confidentiality, we have obtained a Certificate of Confidentiality through the NIH for this research program, which will be amended to include Phase III. The risk of discomfort from discussion of mental health issues, including disclosure of traumatic material is moderate; however, the increased discomfort would be expected to be short-term and participants expressing severe distress would be referred for evaluation and treatment. The identification of a Veteran whose impairment is debilitating is expected to be a low-frequency occurrence. However, should an impaired Veterans be identified in the proposed project, appropriate referrals will be made. The saliva sample may cause embarrassment for some people. The risks of having blood taken from a vein in your arm are pain, bleeding, bruising, and rarely, infection at the site where the needle is inserted. Fainting or light-headedness may occur, but they seldom happen. If the Veteran is injured as a result of having blood drawn, VA will provide medical treatment for his/her research-related injury at no cost to the Veteran. There is a very remote risk that the Veteran's DNA sample might be obtained by someone who has no right to examine it, and enough information might be determined from DNA to identify him/her even if only a code is attached to the sample. There might be identity risks involved if this information falls into the wrong hands (e.g., the Veteran could be denied insurance coverage or employment because of certain genetic information about him/her). Federal laws and policies provide protection from discrimination by health insurance companies, group health plans, and most employers based on genetic information. A new federal law, the Genetic Information Nondiscrimination Act (GINA), will generally provide protection in the following ways: 1) Health insurance companies and group health plans may not request the Veteran's genetic information obtained from this research; 2) Health insurance companies and group health plans may not use the Veteran's genetic information obtained from this research when making decisions regarding his/her eligibility or premiums; and 3) Employers with 15 or more employees may not use the Veteran's genetic information obtained from this research when making a decision to hire, promote, or fire you or when setting the terms of employment. However, this new Federal law does not protect the Veteran against genetic discrimination by companies that sell life insurance, disability insurance, or long-term care insurance.
